16.7.1 Investigator Records

The investigator is responsible for the preparation and retention of the records cited below. All of the below records, with the exception of case history records and case report forms, should be kept in the Investigator Site File (i.e., the study binder provided to the investigator) or Subject Study Binder.

Electronic CRFs must be maintained and signed electronically within the electronic data capture system during the study. The following records are subject to inspection and must be retained for a period of two years (or longer as local law or hospital administration requires) after the date the investigation is completed or terminated or the records are no longer required to support a pre-market approval application, whichever date is later.

- All correspondence between the IRB, sponsor, monitor, FDA, and the investigator that pertains to the investigation, including required reports.
- Subject's case history records, including:
 - Signed and dated IC signed by subject
 - Observations of AEs/ADEs/DDs
 - Medical history
 - Implant and follow-up data (if applicable)
 - Documentation of the dates and rationale for any deviation from the protocol
- List of investigation study sites
- Financial Disclosure
- Subject Identification & Enrollment Log
- Device Disposition Logs containing information similar to model and serial numbers of devices delivered to the study site, subject IDs of the subjects implanted, received dates of devices, implant/used dates, explant dates, returned-to-sponsor dates and reasons, initials of all persons who received, used, or disposed each device, and method of disposal/destruction
- All approved versions of the CIP, IC, Report of Prior Investigation Summary
- Signed and dated CTA
- CV of principal investigators and key members of investigation study site team
- Documentation of delegated tasks
- IRB approval documentation. Written information that the investigator or other study staff, when member of the IRB, did not participate in the approval process.
- FDA notification, correspondence, and approval
- Study training records for study site staff

- Any other records that FDA requires to be maintained
- Final Study Report including the statistical analysis

16.7.2 Sponsor Records

Medtronic shall maintain the following accurate, complete, and current records:

- All correspondence which pertains to the investigation
- Investigational device traceability record containing information similar to model and serial numbers of devices, shipping date and name and address of person that received shipped device, location (if different than person shipped to), transfer and receipt by Medtronic dates
- Sample of label attached to investigational device
- Signed Investigator Trial Agreements, Financial Disclosure and current signed and dated CV of principal investigator and key members of the investigation study site, delegated task list
- All approved IC templates, and other information provided to the subjects and advertisements, including translations
- Copies of all IRB approval letters and relevant IRB correspondence and IRB voting list/roster/letter of assurance
- Names of the institutions in which the study will be conducted
- FDA correspondence, notification and approval as required by national legislation
- Names/contact addresses of monitors
- Monitoring visit reports
- Statistical analyses and underlying supporting data
- Final report of the study
- The CIP, Report of Prior Investigations summary and study related reports, and revisions
- Study training records for study site personnel and Medtronic personnel involved in the study
- Any other records that local regulatory agencies require to be maintained.

Medtronic records and reports will be maintained in a password-protected document management system, and paper documents (where applicable) will be stored in stored in secured file cabinets at Medtronic during the course of this study.

After closure of the study Medtronic will archive records and reports indefinitely.

16.8 Reporting Requirements

16.8.1 Investigator Reports

The investigator is responsible for the preparation (review and signature) and submission to the sponsor of all case report forms, adverse events and adverse device effects, device deficiencies, deaths, and any deviations from the clinical investigation plan. If any action is taken by an IRB with respect to this study, copies of all pertinent documentation must be forwarded to Medtronic in a timely manner. Reports are subject to inspection and to the retention requirements as described above for investigator records.

Investigator reporting requirements are listed in Table 11: Investigator reports applicable per Medtronic requirements. The investigator shall prepare and submit in a complete, accurate and timely manner the reports listed in this section. Table 12: Additional Investigator reports applicable to the United States per FDA regulations lists Additional Investigator reports applicable to the United States per FDA regulations.

Table 11: Investigator reports applicable per Medtronic requirements

Report	Submit to	Description/Constraints
Withdrawal of IRB approval	Sponsor and FDA	The investigator must report a withdrawal of approval by the reviewing IRB of the investigator's part of the investigation within 5 working days.
Study Deviations	Sponsor and IRB	Any deviation from the clinical investigational plan shall be recorded together with the explanation of the deviation. Notice of deviations from the CIP to protect the life or physical well-being of a subject in an emergency shall be given as soon as possible, but no later than 5 working days after the emergency occurred. Except in such emergency, prior approval is required for changes in the plan or deviations.
Final Report	IRBs and FDA	This report must be submitted within 3 months of study completion or termination.

Table 12: Additional Investigator reports applicable to the United States per FDA regulations

Report	Submit to	Description/Constraints
Withdrawal of IRB approval (either suspension or termination)	Sponsor	The investigator must report a withdrawal of approval by the reviewing IRB of the investigator's part of the investigation within 5 working days. (21 CFR 812.150(a)(2))
Progress report	Sponsor and IRB	The investigator must submit this report to the sponsor and IRB at regular intervals, but in no event less than yearly intervals. (21 CFR 812.150 (a)(3)).
Study deviations	Sponsor and IRB	Notice of deviations from the CIP to protect the life or physical wellbeing of a subject in an emergency shall be given as soon as possible, but no later than 5 working days after the emergency occurred. Except in such an emergency, prior approval is required for changes in the plan or deviations. If the deviation may affect the scientific soundness of the plan or the rights, safety and welfare of the subjects, the deviation must be approved by Medtronic, the IRB, and the FDA. If the deviation does not affect these issues, then only Medtronic must approve it. (21 CFR 812.150(a)(4))
Failure to obtain IC prior to investigational device use	Sponsor and IRBs	If an investigator uses a device without obtaining IC, the investigator shall report such use within 5 working days after device use. (21 CFR 812.150(a)(5))
Final report	Sponsor IRBs Relevant Authorities	This report must be submitted within 3 months of study completion or termination of the investigation or completion or termination of the investigator's part of the investigation. (21 CFR 812.150(a)(6))
Other	IRB and FDA	An investigator shall, upon request by a reviewing IRB, FDA, provide accurate, complete, and current information about any aspect of the investigation. (21 CFR 812.150(a)(7))

16.8.2 Sponsor Reports

Medtronic shall prepare and submit the following complete, accurate, and timely reports listed in the tables below (by geography). In addition to the reports listed below, Medtronic shall, upon request of FDA, provide accurate, complete and current information about any aspect of the investigation.

Medtronic reporting requirements are listed in Table 13: Sponsor reports for the United States.

Table 13: Sponsor reports for the United States

Report	Submit to	Description/Constraints
Withdrawal of IRB approval	Investigators, IRB, FDA, and relevant authorities	Notification within five working days. (21 CFR 812.150(b)(2))
Withdrawal of FDA approval	Investigators, IRB, and relevant authorities	Notification within five working days. (21 CFR 812.150(b)(3))
Investigator List	FDA	Submit at six-month intervals, a current list of the names and addresses of all investigators participating in the investigation. (21 CFR 812.150(b)(4)) unless a waiver is granted by FDA.
Progress Reports	IRB and FDA	Progress reports will be submitted at least annually. (21 CFR 812.150(b)(5), 812.36(f))
Recall and device disposition	Investigators, Head of Institution, IRB, relevant authorities, and FDA	Notification within 30 working days and will include the reasons for any request that an investigator return, repair, or otherwise dispose of any devices. (21 CFR 812.150(b)(6))
Final report	Investigators, IRB and FDA	Medtronic will notify FDA within 30 working days of the completion or termination of the investigation. A final report will be submitted to the FDA, investigators, and IRBs within six months after completion or termination of this clinical study. (21 CFR 812.150(b)(7))
Failure to obtain informed consent	FDA	Investigator's report will be submitted to FDA within five working days of notification. (21 CFR 812.150(b)(8))
Study deviation	Investigators	Ensure that all deviations from the CIP are reviewed with the appropriate clinical investigator(s), are reported on the eCRFs and the final report of the clinical investigation. Study site specific study deviations will be submitted to investigators periodically.
Other	IRB, FDA	Accurate, complete, and current information about any aspect of the investigation. (21 CFR 812.150(b)(10))

[figure not shown]
Report	Submit to	Description/Constraints
Premature termination or suspension of clinical study	IRB, Investigators, and FDA	Medtronic will provide prompt notification of termination or suspension and reason(s) to investigator and where required to IRB and FDA.

16.9 Publication and Use of Information

Publications from the Evaluation of Implantable Tibial Neuromodulation (TITAN 2) Pivotal Study will be handled according to Standard Operating Procedures and as indicated in the CTA.

16.9.1 Publication Committee

Medtronic intends to publish the results from the study in a timely manner upon study completion.

16.10 Suspension or Early Termination

Medtronic reserves the right to suspend or terminate the study at any time. Reasons may include, but are not limited to, the following:

- Insufficient enrollment to complete the study within the expected timeframe
- Identification of unacceptable safety profile; suspicion of an unacceptable risk will result in a suspension, confirmation of an unacceptable risk will result in termination
- Inadequate subject adherence to follow-up requirements
- Product performance/product supply issues

Medtronic reserves the right to suspend or terminate the study at an individual site. Reasons may include, but are not limited to, the following:

- Noncompliance with the protocol, including inadequate subject adherence to follow-up requirements
- Serious or repeated deviations at the site
- Failure to implement required corrective and preventive actions
- Insufficient enrollment to complete the study within the expected timeframe
- Loss of appropriately trained site personnel

Investigators are required to notify the IRB and FDA (as applicable) of study suspension/termination. In addition, Investigators should assess whether or not to continue the study based on reasons above. Subjects will be notified by the investigator of suspension/termination due to unacceptable risk or of termination due to any other cause.

17. References

18.1 Informed Consent Materials

Copies of all informed consent materials will be provided to the site under a separate cover.

18.2 Participating Investigators, Institutions & Institutional Review Boards

At the time of completion of the Clinical Investigation Plan, site selection is not yet complete. Therefore, a complete list of names and addresses of the clinical investigators and institutions will be distributed within the Current List of Investigators Report. The complete list of Institutional Review Boards will be provided with the Annual Progress Report.

18.3 Labeling

Copies of the TNM system labeling will be provided to the site under a separate cover.

19. Version History

Version	Summary of changes	Justification of changes	Potential impact of the change on performance, effectiveness, or safety or other endpoints	Identification of the affected study documents	Author(s)/Title
1.0	
• 'Not Applicable, New Document'	Not Applicable	Not Applicable	Not Applicable	REDACTED Clinical Study Manager, Senior Clinical Research Program Manager REDACTED Sr. Principal Biostatistician
2.0	
• Administrative change in wording in "Indication under investigation" in section 3. Synopsis	Not Applicable	None	None	REDACTED Clinical Study Manager, Principal Clinical Research Specialist REDACTED Sr. Principal Biostatistician

Version	Summary of changes	Justification of changes	Potential impact of the change on performance, effectiveness, or safety or other endpoints	Identification of the affected study documents	Author(s)/Title
3.0	
• Inclusion criteria update to require “Failed and/or are intolerant* to at least 2 overactive bladder medications (antimuscarinics or beta-3 agonist) or contraindicated to all pharmacological therapies for the treatment of overactive bladder”• Restriction of OAB medications and advanced therapy treatments through the 12-month follow-up visit• Addition of the 1-month post-explant phone call• Clarification of urinary urge incontinence throughout the document• Additional clarification of missing data handling and the study definition of success, and the addition of sensitivity analyses• Clarification of the power calculations• Modifications to the special considerations for adverse event and/or device deficiency reporting section• Added “Adverse change in bowel and/or urinary function” to Section 11.1 Potential Risks• Clerical and administrative updates	Implementation of FDA feedback, including study design considerations along with ongoing review of risk management documentation	None; study enrollment has not started	IC CRFs	
Clinical Study Manager, Sr. Clinical Research Program Manager
 
Sr. Principal Biostatistician

Version	Summary of changes	Justification of changes	Potential impact of the change on performance, effectiveness, or safety or other endpoints	Identification of the affected study documents	Author(s)/Title
4.0	
Increased sample size from 170 subjects to 200 subjects enrolled (consented) to account for the assumed up to ~40% attrition after consent but prior to the implant procedure (screen failures).Clarifications made to the highest acceptable amplitude the subject should be set to (e.g., ensuring this level is comfortable for the subject) and when the highest acceptable amplitude cannot be found.Removal of reference to legally authorized representatives due to protocol requirements for subject's ability to sign consent.Clarification that no Contract Research Organization(s) will be used for the study.Further definition of the responder rate for OAB.Definition provided for clinical relevance of statistical analysis results.Recommendation included for cultures (when applicable) for suspected infections.Clerical and administrative updates	Ongoing monitoring of screen failure rate, administrative clarifications, and implementation of FDA feedback, including study design considerations	None	IC	
Clinical Study Manager, Sr. Clinical Research Program Manager
 
Sr. Principal Biostatistician

## 1. Version History

Version	Summary of Changes	Author(s)/Title
1.0	

Not Applicable, New Document

	[REDACTED] Distinguished Statistician

**2. List of Abbreviations and Definitions of Terms**

Abbreviation	Definition
ADE	Adverse Device Effect
AE	Adverse Event
BMI	Body Mass Index
CEC	Clinical Events Committee
CIP	Clinical Investigation Plan
CRF	Case Report Form
DD	Device Deficiency
eCRF	Electronic Case Report Form
FAS	Full Analysis Set
FCS	Fully Conditional Specification
FDA	Food and Drug Administration
HRQL	Health Related Quality of Life
ITNM	Implantable Tibial Neuromodulation
ITT	Intent-to-treat
IUSS	Indevus Urgency Severity Scale
LOCF	Last Observation Carried Forward
MedDRA	Medical Dictionary for Regulatory Activities
MI	Multiple Imputation
OAB	Overactive Bladder
OAB-q	Overactive Bladder Quality of Life
PASS	Power Analysis & Sample Size (software)
PMA	Premarket Approval
PTNS	Percutaneous Tibial Nerve Stimulation
PTNM	Percutaneous Tibial Neuromodulation
QoL	Quality of Life
SAE	Serious Adverse Event
SAP	Statistical Analysis Plan
SNM	Sacral Neuromodulation
TNM	Tibial Neuromodulation
UF	Urinary Frequency
UI	Urinary Incontinence
UPS	Urgency Perception Scale
USADE	Unanticipated Serious Adverse Device Effect
UU	Urinary Urgency
UII	Urinary Urge Incontinence

### **3. Introduction**

The medical condition of overactive bladder (OAB) is recognized as a symptom syndrome characterized by the symptoms of urinary urgency (UU), with or without urinary urge incontinence (UUI), usually with urgency frequency (UF) and nocturia (waking at night one or more times to void). Tibial neuromodulation (TNM) devices are designed to deliver electrical pulses that stimulate the tibial nerve that runs posterior to the tibia and extends to the sacral nerve plexus. These pulses are thought to relieve OAB symptoms by modulating communication between the bladder and central nervous system. In order to eliminate the barrier of frequent clinic visits for percutaneous tibial neuromodulation (PTNM) sessions while retaining the effectiveness and positive safety profile of tibial neuromodulation, implantable tibial neuromodulation (ITNM) devices have been proposed as an alternative to PTNM.

The Titan 2 pivotal study is intended to assess the safety and effectiveness of the Medtronic TNM system for the treatment of overactive bladder via a single arm, multicenter, prospective design. This statistical analysis plan (SAP) was created using the clinical investigation plan (CIP) version identified on the cover page and defines the analyses that will be included in the premarket approval (PMA) and final clinical study reports. Study progress reports will generally follow the methods of this SAP but will contain a small subset of planned analyses. Importantly, the progress reports will not include effectiveness results until after the PMA submission has been completed, as no interim assessments of effectiveness are planned for this study. Revisions to the SAP may be required if protocol changes impact the statistical analysis for the study, or if updates to the analyses are needed. In cases where the SAP is not updated, any changes to the planned analyses will be documented in the associated report. The study objectives are taken directly from the CIP.

### **4. Study Objectives**

#### **4.1 Primary Objective**

To demonstrate that the percentage of subjects considered a UUI responder after 6 months of tibial neuromodulation exceeds a performance goal of 40%.

#### **4.2 Primary Endpoint**

Proportion of TNM subjects experiencing a reduction of 50% or more in daily urinary urge incontinence (UUI) episodes (UUI responder rate) at 6 months after device implant.

[figure not shown]
#### **4.3 Secondary Objectives**

- To demonstrate an improvement from baseline to 6 months in number of UUI episodes in subjects with UUI at baseline
- To demonstrate an improvement from baseline to 6 months in number of UF episodes in subjects with UF at baseline

- To demonstrate an improvement from baseline to 6 months in urinary urgency using the Urgency Perception Scale (UPS)
- To demonstrate an improvement from baseline to 6 months in quality of life (QoL) using the Overactive Bladder Symptom Quality of Life Questionnaire (OAB-q)

#### **4.3.1 Secondary Endpoints**

[figure not shown]
- Change in UUI episodes at 6 months compared to baseline in subjects with UUI at baseline
- Change in daily UF episodes at 6 months compared to baseline in subjects with UF at baseline
- Change in urinary urgency assessed through the UPS at 6 months compared to baseline
- Change in OAB-q HRQL (health related quality of life) Total Score at 6 months compared to baseline

## **5. Investigation Plan**

This is a prospective, multicenter, single-arm pivotal study to assess safety and effectiveness for the implantable TNM device in subjects with overactive bladder. Subjects who meet all inclusion/exclusion criteria will be implanted with the implantable TNM device. A full list of eligibility criteria can be found in the CIP. Study visits are shown in Figure 1.

**Figure 1: Study Visits**

## 6. Determination of Sample Size

Sample size determination was made using PASS 2019. The sample size for the primary objective was estimated using a binomial distribution for a one-sided alpha=0.025 test to show a 15% increase for the proportion compared to a performance goal of 40%. Assuming the alternative hypothesis of  $\geq 55\%$  of subjects who are considered an UUI responder, a minimum of 121 implant attempted subjects achieves at least 90% power to reject a performance goal of 40%. The primary objective will have at least 88% power for any alternative hypothesis that is at least 15% larger than a performance goal. Secondary objectives are also expected to be adequately powered based on this sample size.

Assuming a ~40% attrition rate before implant, up to 200 subjects will be consented to achieve at least 121 subjects with implant attempted. Enrollment will be closed once the number of completed implants reaches 121; all enrolled subjects who meet eligibility criteria may be implanted (not to exceed 130 total implants). Implant attempted subjects who exit from the study will not be replaced.

## 7. Statistical Methods

### 7.1 Study Subjects

#### 7.1.1 Disposition of Subjects

Subject disposition will be summarized in a flow diagram by study visit. A summary of subjects included in each analysis set will be provided. Discontinuation will be summarized by visit and discontinuation reasons.

### **7.1.2 Clinical Investigation Plan (CIP) Deviations**

A study deviation is defined as an event within a study that did not occur according to the CIP. The frequency of CIP deviations will be summarized by type of deviation. A summary of deviation type by clinical study center will also be included.

### **7.1.3 Analysis Sets**

All Enrolled analysis set: Includes subjects who completed the informed consent process.

Full Analysis Set (FAS): Includes subjects with an attempted implant. If all implant procedures are successful, this will be equivalent to the All Implanted Analysis set. In the case that all subjects have successful implant procedures, the name 'All Implanted Analysis set' will be used. This is the primary analysis set for both safety and effectiveness .

All Implanted Analysis set: Includes subjects who are implanted.

Complete Case analysis sets: Includes subjects who are implanted and provide outcome measures at both baseline and follow-up visits. This set is defined for each outcome measure at each follow-up visit.

As Treated analysis sets: Includes only those complete case subjects who received stimulation in the period prior to the visit. This set is defined for each outcome measure at each follow-up visit. Subjects will be excluded from the As Treated analysis sets if they meet 1 or more of the following:

- If the subject received zero therapy sessions in the 2 weeks prior to the visit
- If the subject experienced a consecutive 4 week period with zero therapy sessions in the 3 months prior to the visit.

**Note:** In the case of missing daily usage data, all missing usage days will be considered as days where the subject received a therapy session as expected per their current program (i.e., missing usage data will not contribute to meeting the 2 criteria above).

The study requires subjects to have diagnosed UUI to be implanted. For analysis purposes, Urinary Frequency (UF) subjects are those who have  $\geq 10$  urinary frequency episodes per day at baseline and all subjects will be considered to have urinary urgency since all eligible subjects have UUI.

Some supportive, secondary objective, [REDACTED] may use different definitions or subsets of the analysis sets listed above (e.g., changed assumptions for those subjects considered to have either UUI or UF).

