- Any changes to the stimulation should be made within the first five minutes of each therapy session.
- It is recommended that the device is recharged weekly.

Any adverse events and/or device deficiencies will be collected.

6-Month Follow-up Visit:

The 3-day urinary voiding diary should be started approximately one week prior to the study visit. If the diary is not able to be completed prior to the visit, it will be completed immediately following the study visit. The Overactive Bladder Quality of Life Questionnaire (OAB-q), [REDACTED]

Scale (UPS) [REDACTED] will be collected.

Urgency Perception

The subject will have an impedance check and sensory/motor threshold testing done with their foot in the same relaxed position as the time of implant. The subject's sensory and motor threshold will be identified using 20 hertz, 200 microseconds pulse width stimulation and titrating up amplitude until the sensory threshold, highest acceptable amplitude and motor threshold are confirmed. The neurostimulator amplitude should be set to the highest acceptable amplitude. If highest acceptable amplitude is unable to be found, it is recommended to set the amplitude to two times the motor or sensory threshold, whichever is lower. The comfort of the programmed amplitude will be verified while the subject is in expected positions and adjusted for comfort, if needed.

If the sensory threshold, highest acceptable amplitude and/or motor threshold are not observed, this will be documented. The Investigator or delegated personnel should try repeating the motor and sensory assessment with the foot in a different position. If the motor and/or sensory response is still not observed, the Investigator or delegated personnel should set neurostimulator amplitude to 3 mA unless an alternative amplitude level is recommended by the Sponsor.

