At the completion of the 24-month follow-up visit (along with the final voiding diary), the subject will be exited from the study. All programming completed at the visit will be up to the investigator's discretion. Any adverse events and/or device deficiencies will be collected.

The TNM neurostimulator may remain implanted following study exit; the decision whether to explant will be per physician and patient discretion. [REDACTED]

[REDACTED] Subjects should be given instructions to contact the study doctor or research coordinator if any component of the TNM system is lost, damaged or malfunctions following completion in the study.

Follow-up Visit Data Collection:

Table 4 outlines requirements for each follow-up visit, including unscheduled visits. Based on the visit requirements, the following data points may be collected.

For logistical and public safety issues (e.g., global pandemic), remote collection of follow-up data will be allowed along with remote device access/programming with enabling software (as applicable). If available during the study, Medtronic may use remote support to access programming data.

In addition to collection of adverse events, device deficiencies, OAB medications, protocol deviations and study exit data, data points are described, but not limited to, the following sections.

- Post-operative care (e.g., wound healing, compression use, activity level assessment questions, etc.)
- Voiding diary
- Questionnaires: OAB-q, [REDACTED] UPS, [REDACTED]
- Motor and sensory threshold data
- Programming/device/recharge data

Periodic Progress Check-in Calls:

Following the device implant, it is recommended that site personnel contact study subjects within approximately 48 hours after each study visit and approximately one week prior to each upcoming visit. In addition to these calls, monthly check-in calls will be recommended to start following the 3-month follow-up visit. The intent of the call will be to verify the handset "stimulation on" slide button is on,

provide recharge reminders for the handset, communicator and wireless recharger and provide any reminders for upcoming visits (e.g., diary completion).

Any adverse events and/or device deficiencies will be collected.

Unscheduled Visits

An unscheduled visit may be needed for any device-related reason. During the visit, any OAB medication changes, adverse events and/or device deficiencies will be collected. A 3-day urinary voiding diary may be completed.

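### The As Treated set can include subjects with no stimulation before or during the endpoint diary, because missing usage days count as sessions and the look-back ends at the visit

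*SAP*

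**What the plan says.** SAP 7.1.3 defines the As Treated set: "Includes only those complete case subjects who received stimulation in the period prior to the visit". A complete case is removed on either of two criteria: "If the subject received zero therapy sessions in the 2 weeks prior to the visit", or "If the subject experienced a consecutive 4 week period with zero therapy sessions in the 3 months prior to the visit".

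A note then deals with gaps in the usage record: "all missing usage days will be considered as days where the subject received a therapy session as expected per their current program". It spells out the effect: "missing usage data will not contribute to meeting the 2 criteria above". No maximum number of missing days is set, and no alternative version is planned.

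The diary that produces the UUI responder, UUI change and UF change endpoints has its own timing. For the 6-month visit, Protocol 10.1 says: "The 3-day urinary voiding diary should be started approximately one week prior to the study visit". The fallback is: "If the diary is not able to be completed prior to the visit, it will be completed immediately following the study visit". SAP 7.2.2 likewise accepts a diary before or after the visit. Nothing in SAP 7.1.3 links the exclusion windows to the diary dates. The protocol names an As Treated analysis but gives neither the look-back windows nor the missing-day rule.

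**The concern.** The As Treated analysis should show the response among subjects who were actually stimulated. Two of its rules weaken that.

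First, an absent usage record is treated as evidence of therapy. Usage data reach the sponsor by handset transfer or a programming worksheet (Protocol 10.7), so gaps are possible. Each gap moves a subject towards inclusion.

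Second, for the diary endpoints the exposure window and the outcome window do not line up. A session after the diary has ended cannot have affected it, yet it can satisfy the 2-week criterion. When the diary follows the visit, its days are not looked at.

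The trial is single-arm and unblinded, and SAP 7.2.1 itself raises placebo effects. The As Treated set is applied to the primary endpoint, all four secondary endpoints and the long-term results. If it does not separate stimulated from unstimulated diaries, it says less about the therapy than its name suggests.

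**Working it through.** The As Treated rule carries no stated figure. The plan's sample-size figure is not in dispute and reproduces. With an exact binomial test, N = 121, a 40% goal and one-sided alpha 0.025, the null hypothesis is rejected at 60 or more responders (60/121 = 49.6%). The exact alpha is 0.0204 and power at 55% is 0.9009, against the stated minimum of 90%.

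**Inputs**
- Exclusion criteria and missing-day rule: SAP 7.1.3.
- Day grid: visit = day 0. Three months is taken as 90 days (-90 to -1), which is an assumption. Two weeks = days -14 to -1; four weeks = 28 days.
- Diary: days -7 to -5 by default, or days 0 to 2 in the fallback (Protocol 10.1).
- Schedule before 6 months: every other day, as recommended in Protocol 10.7.

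A subject stays in the set if at least one counted session falls on days -14 to -1 and the longest run of days without a counted session is 27 or less.

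**1. Complete usage data, diary before the visit.** Sessions on days -88, -60, -32 and -4 give these session-free runs:
- -90 to -89: 2 days
- -87 to -61: 27 days
- -59 to -33: 27 days
- -31 to -5: 27 days
- -3 to -1: 3 days

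The longest run is 27 (< 28) and day -4 is inside the last 14 days, so the subject is kept. The diary occupies the last 3 days of the run from -31 to -5, leaving 27 - 3 = 24 unstimulated days (-31 to -8) before it. This is the maximum. Restarting on day -3, -2 or -1 instead allows 23, 22 or 21 days plus the 3 diary days.

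**2. Complete usage data, diary after the visit.** With sessions every other day from day -90 to day -14 and none afterwards, the last run is days -13 to -1 = 13 days. The session on day -14 satisfies the 2-week criterion, so the subject is kept. Diary days 0 to 2 lie outside both windows.

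**3. Missing usage data.**
- All 90 days missing: every scheduled day counts as a session, so the subject is kept even if none took place.
- Only days -63, -35 and -7 missing and no session recorded: these days are 28 apart, so all three can fall on a 48-hour schedule. The runs are -90 to -64 (27), -62 to -36 (27), -34 to -8 (27) and -6 to -1 (6). The subject is kept.
- Two missing days are not enough. They span at most 27 + 1 + 27 + 1 + 13 = 69 days, short of 90. An exhaustive search over all pairs confirmed this.

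**4. Would re-anchoring help?** Take a window from 14 days before diary start to diary end.
- Case 1: days -21 to -5 hold no session, so the subject is removed.
- Case 2: days -14 to 2 include day -14, so the subject stays. Only a separate check of the diary days removes this case.
- All usage missing: the subject is removed once missing days count as no session.

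**5. Direction of effect (assumed figures only).** Take 110 subjects in the set and 60% response among those stimulated. With 12 unstimulated subjects responding at 10%, the rate is (98 × 0.60 + 12 × 0.10)/110 = 60/110 = 54.5%. If they respond at 60%, it stays at 60.0%. With 3 to 12 such subjects and response of 10% to 60%, the rate lies between 54.5% and 60.0%. It exceeds 60% only if unstimulated subjects respond more often than stimulated ones.

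**The case against.** The strongest reply is that this is a disclosed, prespecified convention: exclude only on positive evidence of non-use. The note states its own effect, and the opposite rule would drop treated subjects because a data transfer failed. That stands as a reason to keep the present rule as one version. It does not justify having it as the only one.

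The set also does real work. With usage recorded, a subject with no session in the 2 weeks before the visit, or with a 4-week gap in the 3 months, is removed. A reader might infer that As Treated must reproduce the complete-case result whatever the adherence. That is not so for recorded non-users.

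The anchor problem does not reach every endpoint. UPS and OAB-q are completed during the visit (Protocol 10.10), so the visit is a suitable anchor for them. Only the missing-day rule affects those two.

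A reader might also suppose that usage is missing because the device is depleted, or that the check-in call recommended "approximately one week prior to each upcoming visit" prompts lapsed subjects to restart just after the diary. The call is meant to verify that stimulation is on, but it and the diary start are both about a week before the visit, and nothing places a restart after the diary. Calls are also recommended within about 48 hours after each visit and monthly after Month 3, which makes a long unnoticed lapse less likely. The documents do not say how often usage data are missing, or why.

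It is also true that three sessions in 90 days can satisfy both criteria, against 90/2 = 45 on the every-other-day schedule. That follows from the 2-week and 4-week thresholds, not from the anchor or the missing-day rule, and re-anchoring would not change it.

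Finally, As Treated is not the only look at exposure. SAP 7.9.1.1 compares responder rates between stimulation programs and SAP 7.7 summarises usage, although neither restricts the outcome analysis to subjects with delivered stimulation.

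**Conclusion.** The point holds as a limitation of a sensitivity analysis. As written, the As Treated set can include subjects with no stimulation before or during the endpoint diary. With complete usage data and the default diary timing, the unstimulated stretch can reach 24 days before the diary plus its 3 days. With a diary after the visit, it can be 13 days before the visit plus diary days that are never examined. With missing usage data there is no limit. These figures rest on 3 months being 90 days and on the nominal diary days; they describe what the rule permits, not how often it will happen.

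A reader might infer that the rule favours the device by crediting placebo response to it. The documents do not support a direction: including unstimulated subjects may equally dilute the observed response, and the number affected is unknown. Trial success rests on the primary objective in the Full Analysis Set, and the SAP sets no result that the sensitivity analyses must reach. The primary test, alpha, N = 121 and power are unaffected. The change is worth making because it is cheap and lets the analysis isolate stimulated subjects better.

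**What to change.** Amend SAP 7.1.3 as follows.

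- **Diary endpoints (UUI responder, UUI change, UF change):** tie both windows to the diary dates, so that sessions after the diary ends cannot qualify a subject. Also check the diary days themselves. Make that check against the sessions scheduled on those days, because Protocol Table 2 includes a once-weekly option under which a 3-day diary may contain none.
- **UPS and OAB-q:** keep the visit as the anchor.
- **All endpoints:** report the number of missing usage days, and add a second As Treated version that counts missing days as no session. Shown beside the present rule, it reveals how far the result depends on that rule.
- **Usage summary in SAP 7.7:** tabulate sessions delivered over sessions scheduled.

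Diary start and end times and usage reports are already collected. One limit is that a report taken at the visit cannot cover a diary kept afterwards. Those days need a later data transfer, or they count as missing and are handled by the two versions.

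The cost is SAP wording, a little programming and a somewhat smaller set. The second version may drop some subjects who were treated but whose data were not transferred. No visit or treatment changes.
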